Data and/or Specimen Location: All PHI data will be stored on the VA server at S:\GRECC\Grecc Research\[name]\Valor Up that is encrypted, password-protected, and only accessible to [name] and her study staff. All hard copy data, including, but not limited to, consent form, HIPAA authorization form, and survey responses will be stored in a locked file cabinet in a locked office suite at the Duke Aging Center Nutrition Laboratory, Room 00505. Data will be entered using VPN access by the VA Research team.

The study team will employ REDCap (Research Electronic Data Capture) hosted within VIREC for data entry. Key components of this activity include data entry screen programming and database testing and validation.

The database will include study default parameters and ranges for database, protocols, users, and access rights. Access and data entry to the database will be controlled by login permissions, and the database will be backed up daily, with full backups occurring weekly, and quarterly backups retained for perpetuity.

A second excel spreadsheet database will be created to electronically track participants through all components of the study including screening. This tracking will contain identifiable data, including the key that links participants to study identification numbers; other data collected in the course of the study will be kept separately from identifying information. This database will be stored on the VA server S:\GRECC\Grecc Research\[name]\Valor UP. that is encrypted, password-protected, and only accessible to [name] and her study staff.

Plasma specimens will be stored in the -80 degree freezer at the Duke Center for Living. Specimens, as outlined above, will be coded when stored.

Data will be also be placed at the VA Informatics and Computing Interface (VINCI); <http://vaww.vinci.med.va.gov/vincicentral/VINCIWorkspace.aspx>). The VA Informatics and Computing Infrastructure is a partnership between the VA Office of Information Technology and the Veterans' Health Administration Office of Research and Development. Researchers and operations staff can use VINCI to access data and statistical analysis tools in a virtual working environment through a certified VHA network computer using the VA Intranet or Virtual Private Network (VPN).

B. Data Retention Plan

Research records will be maintained and destroyed according to the National Archives and Records Administration, Records Schedule Number: DAA-0015-2015-0004. Records destruction, when authorized, will be accomplished using the then current requirements for the secure disposal of paper and electronic records. Currently, destruction of research records (see DAA-0015-2015-0004, section 7.6 "Research Investigator Files" for materials included in research records) is scheduled for 6 years after the cut-off (the cut-off is the completion of the research project) and may be retained longer if required by other federal agencies. Records will not be destroyed without pre-notification to the facility records manager.

Other data retention plan, describe:

4. Data Access and Data Recipients: Only members of our DVAMC research team will have access to identifiers and coded data. Our statistician, [name] will have access to the de-identified data. All VA research personnel who have access to VHA records are instructed, in accordance with VA policy, on the requirements of Federal privacy and information laws and regulations, VA regulations and policies, and VHA policy. All study personnel who are VA employees working within the VA system have fulfilled all required HIPAA and other VA security and privacy policy training requirements and have agreed to follow guidelines pertaining to the protection of patient data. All research staff sign VA Rules of Behavior, and all study staff are up-to-date with VHA Privacy Policy Training and the VA Office of Cyber and Information Security Awareness Training Course. The data security and privacy procedures summarized in that course include logging off or locking the computer when walking away from it; no sharing of access codes, verify codes or passwords; not allowing anyone else to use the computer under one's password; and disposing of sensitive information using VA-approved methods (e.g., shredder bins).

Access to study data will be removed for all study personnel when they are no longer part of the research team.

5. Data and/or Specimen Transportation and/or Transmission for all data and/or specimens involved in the study:

- I. Data and/or specimens will not be transported or transmitted outside of Durham VAMC environment.
- II. Data and/or specimens will be transported BETWEEN sites that are under the auspices of the Durham VA Medical Center.
- III. Data and/or specimens will be transmitted to other VA sites using the following method(s):
 - A. **Data**
 - Data are de-identified and thus will be sent via unencrypted e-mail or unencrypted disk (encryption is optional).
 - Data are coded or contain identifiers and thus will be sent
 - Other, describe:
 - B. **Specimens**
 - Specimens are de-identified and thus will be sent via standard carrier (tracking is optional).
 - Specimens are coded or contain identifiers and thus will be sent via VA-authorized carrier with tracking.
 - Other, describe:
- IV. Data and/or specimens will be transported to non-VA/VHA sites (e.g., academic affiliates, laboratories, etc.) using the following method(s):
 - A. **Data**
 - Data are de-identified and thus will be sent via unencrypted e-mail or unencrypted CD.
 - Data are coded or contain identifiers and thus will be sent via FIPS 140-2 encrypted hard drive/flash drive using VA—approved carrier with tracking.
 - Data are coded or identified and will be uploaded to sponsor website using electronic case report form (eCRF)
 - Other, describe: Data will be stored at the Duke Aging Center Nutrition Laboratory. Data will only be transferred to the VA if the Durham Office of Research and Development deem it necessary. In this event, data will be transferred using a FIPS 140-2 encrypted hard drive/flash drive and walked over to the VA by a member of the research team
 - B. **Specimens**
 - Specimens are de-identified and thus will be sent via standard carrier (tracking is optional) or will be hand-delivered by research study personnel. Specify method of delivery:
 - Specimens are coded and thus will be sent via VA-approved carrier with tracking or will be hand-delivered by research study personnel. Specify method of delivery: Specimens will be analyzed through the Duke Molecular Physiology Institute. Co-Investigator, [name], will oversee the transfer of specimens from the Duke Center for Living to the Duke Molecular Physiology Institute. Specimens will be hand-delivered by members of the research team.
 - Other, describe: Specimens will be stored at the Duke Center for Living in a secured building that requires badge access to enter.

In accordance with the HIPAA and the Privacy Act, for any coded or identifiable data or specimens released from the Durham VAMC (with the exception of Limited Data Sets), an Accounting of Disclosure (AOD) will be maintained (e.g., in a database or spreadsheet) that includes the participant's name, date of the disclosure, description of the nature of the Individually Identifiable Information (III) disclosed, purpose of each disclosure, and the name and address of the person/agency to whom the disclosure was made.

C. Local DVAMC memorandum "Authorization to Use, Process, Store, or Transmit VA Sensitive Information Outside VA Owned or Managed Facilities" has been pre-filled out for each study team member who may transport the data and/or specimens off-site. This (these) forms are included with the IRB materials.

D. Containers (e.g., briefcase, bin) are labeled with the following notice (label placed on the outside of container) in accordance with VHA Directive 6609:

NOTICE!!!

Access to these records is limited to: AUTHORIZED PERSONS ONLY.

Information may not be disclosed from this file unless permitted by all applicable legal authorities, which may include the Privacy Act; 38 U.S.C. §§ 5701, 5705, 7332; the Health Insurance Portability and Accountability Act; and regulations implementing those provisions, at 38 C.F.R. §§ 1.460 – 1.599 and 45 C.F.R. Parts 160 and 164. Anyone who discloses information in violation of the above provisions may subject to civil and criminal penalties.

V. We will communicate with veterans enrolled as participants in this research study through Myhealthe.va.gov .

6. Risk Mitigation Strategies:

At each level of data management and for each subject contact, strict adherence to VHA policy will be observed regarding HIPAA, IRB, and other VHA patient quality controls. A unique code number will be assigned to each participant. The key to the code will be kept in a password-protected file on a secured network S:\GRECC\Grecc Research\[name]\Valor Up We will employ REDCap (Research Electronic Data Capture) hosted within VIRECfor data entry. Key components of this activity include data entry screen programming and database testing and validation. The database will include study default parameters and ranges for database, protocols, users, and access rights. Access and data entry to the database will be controlled by login permissions, and the database will be backed up daily, with full backups occurring weekly, and quarterly backups retained for perpetuity.

As previously described, a second excel spreadsheet database will be created to electronically track participants through all components of the study including screening. This tracking will contain identifiable data, including the key that links participants to study identification numbers; other data collected in the course of the study will be kept separately from identifying information. This database will be stored on a Duke secured computer server S:\GRECC\Grecc Research\[name]\Valor Up that is encrypted, password-protected, and only accessible to [name] and her study staff.

These procedures will protect the identity of all patients and providers as pertains to any reports generated from this study. The individuals responsible for data safety and monitoring will be Drs. [name], [name], [name], [name], and [name].

- Data are fully de-identified (stripped of HIPAA 18 and study ID/code) before being shared outside of Durham VAMC.
- Specimens are fully de-identified (stripped of HIPAA 18 and study ID/code before being shared outside of Durham VAMC.
- Direct identifiers will be maintained separately from data and or specimens by using a code to "identify" subjects. In a separate database (i.e., a "linking" or "cross-walk" database) this code will be linked to identifying subject information.
- Other, specify:

7. Suspected Loss of VA Information:

Should any incident such as theft or loss of data, unauthorized access of sensitive data or non-compliance with security controls occur it will be immediately reported according to VA policy. All incidents regarding information security/privacy incidents will be reported to the ISO and PO within 1 hour of acknowledgement of issue and done so using the VHADUR Research Events Report e-mail group

[\([contact]\)](mailto:[contact]).

8. Reporting of Results:

- Reporting of results, such as in scientific papers and presentations, will never identify individual subjects. Data will be presented in aggregate and individual-level data will not be published.
- Other results reporting plan, describe:

9. Future Use of Data:

- Data will be retained for future use. This is described elsewhere in the protocol and is noted in the HIPAA authorization.

- Future Use of data is optional (i.e., not required by the research subject).
- Future Use of data is required for participation in the study.

- No future use of data is currently planned.

10. Use of Mail Merge Technology

- Mail merge programs will be used to generate letters and/or address labels for mailings to potential or already enrolled research subjects. The study team is aware that to reduce risk of mail merge related privacy incidents, use of mail merge programs requires a 25% accuracy check to verify that (potential) research subject name and mailing address are properly "matched". If discrepancies are found, a 100% accuracy check is required before letters may be mailed.

11. Use of Non-Standard Software

- I do NOT intend to use any new specialized software (i.e. Software that's not already approved OR installed) in this study.

- I intend to use specialized software that has not already been installed and it has been approved for use by the VA Technical Reference Model (TRM) Group.

(Note: All new software must be approved by TRM before it can be installed on VA systems.)

- I intend to use previously installed software on my VA computer.

12. Use of Cloud Computing Services

- Cloud computing services will NOT be used in this study.

Cloud computing services WILL be used in this study as described below and have been approved nationally by the VA Chief Information Officer (CIO). (Note: ONLY cloud computing services that have been approved nationally may be used.)

References

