Setting: Screening, baseline, outcome testing and intervention meetings will be conducted at the Sarah W. Stedman Center for Nutritional Studies on the Center for Living Research and Wellness campus at Duke University. Diet and exercise classes will be offered virtually via WebEx or in person at the Center for Living campus. Anthropometrics, functions tests, and blood collection will take place in the Clinical Research Unit there or may be conducted virtually if needed. The Isokinetic knee extension peak torque testing and BodPod body composition measurements will be done in the Sports Sciences Institute, which is adjacent to the Stedman Building. The thigh CT scans will be conducted in Radiology at the Veterans Affairs Medical Center in Durham.

We will enroll participants until we reach a total of 112 study completers. We anticipate enrolling approximately 160, allowing for a 30% dropout rate.

Study Arms:

- **Arm 1: WL-Control (n=56 completers)**
10%* WL diet with 0.8 g protein/kg body wt/day
- **Arm 2: WL-Pro (n=56 completers)**
10%* WL diet 1.4 g protein/kg body wt/day; \geq 30g high quality protein per meal

**Participants enrolled after 10/1/2023 will participate in a shortened study period of 3 months, with only 0 and 3 month assessments for most measures, as noted in the added footnotes below. Their weight loss prescription will be targeted to an expectation of at least 5-10% loss of body weight.*

Measurements:

After the participant has been consented and HIPAA Authorization forms have been signed, screening and baseline assessments will be conducted:

Screening process:

Screening Visit : Consent; confirm BMI ≥ 30 kg/m², confirmed SPPB score of 4-11, confirmed fasting plasma glucose ≥ 95 and < 126 mg/Dl or A1c between 5.7-6.4 (will be confirmed with LapCorp results), and confirmed Mini-Cog score ≥ 3 (if less than 3, confirm participant can conduct all ADLs).

Upon the completion of all baseline assessments (see below), the study biostatistician will then use permuted-block randomization to assign participants to WL-Control or WL-Protein groups. The following variables will be blocked in this order: 1) Race (white versus non-white, 2) Couple/Single status. An equal number of participants will be randomized across the two arms to end up with N=84 (42 black and 42 white) in each arm.

Measures and Data Collection Points

Primary outcome: Physical function (SPPB)

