The calorie level for a weight loss of ~1-2 pounds (average of 0.6 kg) per week will be calculated, generally a reduction of 500 to 1000 kcal/day. The intervention diet will be culturally tailored to meet the individual preferences of the target population and adapted to make sure low-income participants are able to afford the healthy foods in their diet plan. After 2 individual sessions, participants will continue to be submit their weights each week and attend weekly group sessions that provide a curriculum designed to enhance diet compliance ⁵⁰; this includes group support, goal setting, self-monitoring, stress management, problem solving, and relapse prevention, daily diet journaling, email/phone reminders, and tutorials for on-line tools during the entire 6-month intervention. (It should be noted that for participants enrolled after 10/1/2023, the study period will be 3 months instead of 6.) To insure a supportive weekly group size, we will wait to begin the intervention until the first cohort has at least 5 participants in each arm.

Nutritional adequacy will not be compromised; protein intakes are adequate in both arms and the diet pattern will be rich in essential vitamins and minerals ⁵². Additionally, daily low dose multivitamin/mineral supplement, and calcium/vitamin D supplement will be provided, based on menu nutrient content and to achieve consistency (no other supplements permitted unless prescribed by physician).

Physical activity and falls-prevention components of the intervention: Participants in both groups will attend a weekly session of safe, low intensity exercises to encourage safe progression to a more functional lifestyle, including individualized exercise prescriptions for those with military-acquired or other limitations. Instructions will be provided for safe repetition of the exercises at home on at least 2 more days per week. Additionally, weekly support group sessions will include training on falls reduction and safe ways to become more physically active.

WL-Control Diet: 0.8 g protein per kg body weight. Participants will receive careful guidance for consuming only 15% of total calories from protein per day. Expressed another way, control participants will consume about ~0.8 g protein per kg body weight. Each week, participants will be provided 7 servings of whey protein

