powder (15 g/serving) to support diet affordability and provided recipes for low calorie smoothies. The whey protein will be portioned by our research staff and delivered to the participants weekly on Duke's campus.

WL-Protein Diet: 1.4 g protein/kg body weight/day, ≥ 30 g of high-quality protein per meal. Subjects will receive careful guidance for evenly distributing ≥ 90 g high-quality protein between 3 meals plus snacks per day. Each meal includes ≥ 30 g high quality protein, provided directly to WL-Protein for two of three meals daily plus 1 snack, as lean red meats, whey protein, a high-protein milk-based, lactose-free beverage, and chicken. Twenty-one servings of high quality (30 g/serving) protein (lean red meats, whey protein, a high-protein milk-based, lactose-free beverage, and chicken) will be provided to participants each week to increase compliance and enhance affordability. Weighed, individual servings will be chilled or frozen, and delivered to the participants at weekly group meetings in thermal bags. For those unable to transport the bags or using public transportation, delivery to the home will be arranged. The 30 g high quality protein for the third meal of the day will be per participant's choice.

Food record data analyses from previous studies indicates the WL-Control group will be consuming a typical American quantity/ distribution of protein (mean of 22 g per meal with range of 11-30 g), while the WL-Protein group will be consuming the target intake of ≥ 30 g per meal.

Supplemental Project Research Protocol: Feasibility and Acceptability of a Remote Obesity Intervention for Prediabetes: Improving Function on Older Veterans at high Risk During COVID-19 Isolation

Background and Project Summary:

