This design is a two-armed clinical trial, with replicate measures at three time points: baseline, three, and six months. Since subjects are randomized to either WL-Control or WL-Protein arm, and the groups are presumed equal at baseline, the analysis is straightforward. Following the Good Clinical Practice Guidelines for the analysis of a clinical trial, we will employ mixed models, analyze under an Intent to Treat (ITT) criteria, and control for baseline and assess the impact of Time, Treatment Group and the interaction of these variables on the outcomes. Relative to the usual repeated measures designs, mixed models have several advantages: 1) missing values present no particular difficulties in estimation and the estimates are unbiased as long as the set of variables leading to MAR are estimated, 2) the usual assumption of conditional independence (compound symmetry) used in standard repeated measures need not be made, and 3) the actual times of measurement need not be equivalent across subjects. Controlling for the individual baseline values for the particular outcomes, the trajectories over time and differences in those trajectories will be assessed. Following the statistical principles section from the International Conference on Harmonization, we will select covariates (e.g., age, race, number of comorbidities) for the primary models a priori, but we also will conduct auxiliary sensitivity analyses that evaluate whether potential group imbalances bias the treatment effect estimate. These analyses will be performed using conventional testing for confounding. We note that we have listed numerous measures to be analyzed as outcomes, but have listed only 1 primary outcome (physical function, Aim 1).

For any particular outcome, the general form of the model will be:

$$Y_{it} = \beta_0 + \beta_1(\text{group}) + \beta_2(\text{time}_t) + \beta_3(\text{group} * \text{time}_t) + \beta_4(\text{covariates}) + \epsilon_{it}$$

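### If weekly support groups are formed by arm, as the start rule implies, the primary model lacks a group term and any positive within-group correlation makes the diet-effect standard error too small

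*Combined protocol and SAP*

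**What the plan says.** Randomisation is individual. Under Screening process, "the study biostatistician will then use permuted-block randomization to assign participants to WL-Control or WL-Protein groups".

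Delivery is largely in groups. Under Caloric Prescription, Diet Monitoring and Exercise Intervention for Both Arms, men have two individual sessions and then "attend weekly group sessions that provide a curriculum designed to enhance diet compliance". The start rule in the same paragraph is that "we will wait to begin the intervention until the first cohort has at least 5 participants in each arm", and the reason given is to secure a supportive weekly group size. Under WL-Protein Diet, the protein foods are "delivered to the participants at weekly group meetings in thermal bags", while the control whey powder is described separately as handed over weekly on campus. The exclusion criteria rule out men with a psychiatric condition that would keep them from a group intervention setting. There is also an exercise component: "Participants in both groups will attend a weekly session of safe, low intensity exercises".

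Under Analysis Plan for the parent protocol (Aims 1 and 2), "the general form of the model will be" a regression on group (meaning arm), time, their interaction and covariates, with one residual indexed by person and time. The example covariates are age, race and number of comorbidities. The stated advantages of mixed models concern missing data, within-person covariance and unequal visit times. The supplemental protocol repeats this strategy. The Power Estimate section uses 100 men, evenly split, with no allowance for clustering. No section mentions clustering, an ICC or a design effect.

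**The concern.** A minimum counted per arm secures weekly group size only if the groups are made up within arms. In that case men who meet weekly for months, sharing peers and group problem solving, are all on the same diet. Whatever makes one support group do better than another then becomes part of the difference between arms. Individual randomisation does not prevent this, because the correlation arises afterwards.

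A model that knows only persons and visits treats this between-group variation as if it averaged out over men, when it averages out only over groups, of which there are few. The estimated diet effect is not biased by this, but its confidence interval is too narrow and the test of the primary SPPB outcome rejects a true null hypothesis too often.

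**Working it through.** **Inputs from the Power Estimate section:** change in SPPB +2.4 and +0.9 units, difference 1.5; SD of change 1.7; 100 men, 50 per arm; two-sided alpha 0.05; stated power above 99%; stated detectable difference at 80% power 0.96 units, or 0.57 SD. **From Setting and Study Arms:** 112 completers, 56 per arm.

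**Assumed, because the documents do not give them:** ICC 0.01 to 0.05, with 0.10 as an outer case; group size m = 5 to 10, where 5 is the stated minimum.

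**Reproducing the plan.** The standard error is 1.7 × √(2/50) = 0.34. The detectable difference is 0.34 × (1.960 + 0.842) = 0.95 by the normal approximation and 0.96 (0.57 SD) with the t distribution. Power for 1.5 units is 99.3% (normal) or 99.2% (t). The stated figures hold, with a design effect of 1.

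**Allowing for arm-specific groups.**
- Design effect: DE = 1 + (m − 1) × ICC.
- True standard error divided by reported standard error: √DE.
- Actual size of the unadjusted test: 2 × [1 − Φ(1.96/√DE)].
- Detectable difference on 100 men: 0.96 × √DE.
- Power for 1.5 units on 100 men: by the normal approximation, and by t with degrees of freedom equal to the number of groups minus 2. That is 18 for groups of 5 (10 groups per arm) and 8 for groups of 10 (5 per arm).

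| m | ICC | DE | SE ratio | Type I error | Detectable difference | Power for 1.5: normal / t on group df |
|---|---|---|---|---|---|---|
| 5 | 0.01 | 1.04 | 1.02 | 5.5% | 0.98 | 99% / 98% |
| 5 | 0.05 | 1.20 | 1.10 | 7.4% | 1.05 | 98% / 97% |
| 10 | 0.01 | 1.09 | 1.04 | 6.0% | 1.00 | 99% / 96% |
| 10 | 0.05 | 1.45 | 1.20 | 10.4% | 1.16 | 96% / 89% |
| 10 | 0.10 (outer case) | 1.90 | 1.38 | 15.5% | 1.32 | 89% / 80% |

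Simulating the unadjusted t test (40,000 trials per scenario) gave type I error of 5.5% (m = 5, ICC 0.01), 7.2% (5, 0.05), 10.3% (10, 0.05) and 15.7% (10, 0.10), in line with the formula.

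**With the planned 112 completers.** At 56 per arm and DE = 1 the detectable difference is 0.908 units (t). The stated 0.96 therefore survives up to DE = (0.96/0.908)² = 1.12, for example groups of 5 with ICC 0.03 (1 + 4 × 0.03). At DE = 1.45 it is 0.908 × 1.204 = 1.09. The type I error column does not depend on the number of men.

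These figures are for a single comparison of the arms on change in SPPB. The plan's overall test is a joint two-degree-of-freedom test, whose size has not been computed here.

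**The case against.** The strongest reply is that arm-specific groups are inferred. No sentence says that sessions are held separately by arm, the start rule covers only the first cohort, and handing out food at a meeting does not make the meeting exclusive to one arm. The exercise classes could be mixed. If arms share sessions, shared effects largely cancel in the arm contrast. This stands as a limit on confidence. A per-arm minimum set to secure weekly group size is still hard to read any other way.

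A reader might also infer that all support is given in groups. The documents do not support that: calorie and exercise prescriptions are individual, there are email and phone reminders and some one-to-one help, and protein is prescribed per kilogram and supplied in individual servings.

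Nor do they show that calendar period or interventionist is nested in arm. The start rule has both arms of the first cohort begin together, so a calendar effect common to both largely cancels, and no section assigns an interventionist to a group or arm. Peer effects are the main remaining route.

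The printed formula is labelled a general form and could be called schematic. However, the surrounding text deals only with repeated measures within a person, and the power calculation does assume independence. Finally, the size of the problem rests on assumed ICCs and group sizes. At the low end of the range it is about 2% of the standard error.

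**Conclusion.** The concern holds conditionally. If support groups are arm-specific and outcomes within a group are positively correlated, the planned primary analysis reports a standard error that is too small. Over the assumed range (groups of 5 to 10, ICC 0.01 to 0.05) the true standard error is 1.02 to 1.20 times the reported one and type I error is about 5.5% to 10.4%. The documents allow no narrower statement.

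It would be tempting to conclude that the trial is underpowered. The documents do not support that. Over the same range, power on 100 men for the 1.5-unit pilot effect is about 96% or more by the normal approximation and about 89% or more with group-based degrees of freedom. The 0.96-unit detectable difference is optimistic on 100 men, but with 112 completers it survives a design effect up to about 1.12. The case for changing the plan rests on the validity of the primary test and interval. The change should be made before analysis, but the point does not call the design into question.

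**What to change.** - State whether weekly support groups, and separately the exercise classes, are held by arm or mixed.
- Record each man's support group, and define membership in advance as the group he was placed in at the start of group sessions, so that later moves do not alter it.
- In the primary SPPB model, add a random intercept for support group nested in arm, alongside the within-person covariance, with small-sample degrees of freedom such as Kenward-Roger. Report the estimated ICC.
- Restate the detectable difference over a range of ICCs, on the number of men actually planned for analysis.
- If sessions mix arms, say so and do not nest the group term in arm.
- In the 42-man supplement, use the group term only as a sensitivity analysis. If its 21 men per arm form their own groups, sizes of 5 to 10 give only about 2 to 4 groups per arm, too few to estimate a variance component well.

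The cost is a short addition to the analysis plan and one extra variable. The documents describe no attendance list, so membership for men already treated may have to be reconstructed, which becomes harder with time. The statistical price is wider intervals and fewer degrees of freedom because groups are few. With 10 groups (8 degrees of freedom) the critical t is 2.31 rather than 1.98, so intervals could be about 16% wider even if the ICC were zero.
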